7.6.6 Vital Signs

Vital signs measures include HR, BP, respiratory rate, and temperature. Weight will also be measured.

Vital Sign Measurements (Heart Rate, Blood Pressure, Respiratory Rate, Temperature)

Subjects should be resting in a quiet setting without distractions in a semirecumbent position for at least 5 minutes before having vital sign measurements obtained. Supine or seated positions are also acceptable (per site standard procedures) as long as the position used is consistent across subjects at a given site. Vital signs will include HR, systolic and diastolic BP, respiratory rate, and body temperature at timepoints indicated in the SOEs. The correct size of the BP cuff and the correct positioning on the subject's arm is essential to increase the accuracy of BP measurements.

All HR and BP will be taken as a single measurement.

Body Temperature

Body temperature will be measured. The same method must be used for all measurements for each individual subject and should be the same for all subjects enrolled at a site.

7.6.7 Physical Examination

Physical examinations should include assessments of the following body parts/systems: abdomen, extremities, head (eyes, ears, nose, and throat), heart, lungs, neck, neurological, and skin.

An abbreviated or targeted interim physical examination may be done to assess areas with previously noted abnormalities and/or that are associated with any new complaints from the subject.

7.6.8 Pregnancy Testing

For WOCBP, a serum or urine beta human chorionic gonadotropin (β -hCG) pregnancy test will be performed at screening and before dosing. A negative pregnancy result is required before the subject may receive study drug. Additional pregnancy testing will be performed as specified in the SOEs in [Appendix 1](#).

7.7 Appropriateness of Measurements

The safety measures that will be used in this trial are considered standard procedures for evaluating the potential adverse effects of study medications. Immunogenicity is commonly assessed for biologics; therefore, standard tests will be performed to detect the possible presence of specific antibodies to PT101. Pharmacokinetic assessments are also frequently employed in clinical studies to help characterize dose-exposure-response relationships.

Standardized and internationally accepted criteria for the evaluation of UC will be used to assess disease activity in this study, including the Mayo Score, the Geboes score, the RHI, and UC-100 ([Jairath, 2019](#); [Jauregui-Amezaga, 2017](#); [Magro, 2020](#); [Mosli, 2017](#); [Pai, 2019](#)). The PRO and quality of life instruments used in this study are standardized questionnaires that have been widely used in clinical trials in multiple countries ([Irvine, 1994](#); [Ware and Sherbourne, 1992](#); [Yalcin and Bump, 2003](#)).

8 DATA QUALITY CONTROL AND QUALITY ASSURANCE

8.1 Site Training and Monitoring Procedures

A study manual with instructions for study compliance and eCRF completion will be provided. Prior to the enrollment of subjects at the site, the Sponsor or its designated clinical and medical personnel will review the following items with the Investigator and clinic staff:

- The protocol, study objectives, eligibility requirements, study procedures, registration and withdrawal processes
- Current Investigator's Brochure/ package insert
- Recording and reporting AEs and SAEs
- Enrollment goals and study timelines
- The eCRF completion process and source documentation requirements
- Monitoring requirements
- IRB/IEC review and approval process
- Informed consent process
- Good clinical practice guidelines and related regulatory documentation requirements
- Key study team roles and responsibilities
- Investigational product storage, accountability, labeling, dispensing and record keeping
- Subject coding and randomization (if applicable)
- Study samples/specimen collection, handling and shipping
- Protocol compliance
- Clinical study record keeping, document retention, and administrative requirements

Monitoring visits will occur periodically, with frequency dependent on the rate of enrollment and workload at each site. During monitoring visits, the Sponsor representative will review regulatory documentation, eCRFs, source documentation, and investigational product storage, preparation, and accountability. The eCRFs will be reviewed for completeness, adherence to the provided guidelines, and accuracy compared to the source documents. The investigators must ensure that the monitor is allowed to inspect all source documents pertinent to study

subjects, and must cooperate with the monitor to ensure that any problems noted in the course of the trial are resolved. The Investigator must maintain a comprehensive and centralized filing system of all study-related documentation that is suitable for inspection by the Sponsor or its designated monitors and by quality assurance auditors, or representatives of regulatory authorities.

8.2 Data Management Procedures

The Sponsor will provide CRF Completion Guidelines for eCRF data entry. Study specific data management procedures will be maintained in the data management plan. Queries resulting from edit checks and/or data verification procedures will be posted electronically in the eCRF.

8.3 Access to Source Data

The Investigator will permit the Sponsor's representatives to monitor the study as frequently as the sponsor deems necessary to determine that protocol adherence and data recording are satisfactory. Appropriate measures to protect patient confidentiality are to be employed during monitoring. The eCRFs and related source documents will be reviewed in detail by the monitor at each site visit. Original source documents or certified copies are needed for review. This review includes inspection of data acquired as a requirement for participation in this study and other medical records as required to confirm that the information contained in the eCRFs, such as disease assessments, AEs, and concomitant medications, is complete and correct. Other study records, such as correspondence with the sponsor and the IRB/IEC and screening and drug accountability logs will also be inspected. All source data and study records must also be available for inspection by representatives of regulatory authorities.

8.4 Accuracy and Reliability of Data

Steps to be taken to assure the accuracy and reliability of data include:

- The selection of qualified Investigators and appropriate study centers.
- Review of protocol procedures with the Investigators and associated personnel prior to the study.
- Periodic monitoring visits by the designated monitor(s).
- eCRFs will be reviewed for accuracy and completeness by the designated monitor(s) during monitoring visits to the study centers. Any discrepancies will be resolved with the Investigator or designees as appropriate.

8.5 Quality Assurance Procedures

The Sponsor or its designee may conduct audits at the clinical site or other study-related facilities and organizations. Audit reports will be retained by the Sponsor as part of the written record.

8.6 Data Handling and Record Keeping

8.6.1 Data Handling

It is the Investigator's responsibility to ensure the accuracy, completeness, legibility, and timeliness of the data reported to the Sponsor in the eCRFs and in all required reports. Data reported on the eCRF that is derived from source documents should be consistent with the source documents or the discrepancies should be explained.

Any change or correction to an eCRF will be maintained in an audit trail within the electronic data capture system. Data changes may only be made by those individuals so authorized. The investigator should retain records of the changes and corrections, written and/or electronic.

8.6.2 Investigator Record Retention

The Investigator shall retain study drug disposition records and all source documentation (such as original ECG tracings, laboratory/histopathology reports, inpatient or office records) for the maximum period required by the country and institution in which the study will be conducted, or for the period specified by Sponsor, whichever is longer. The Investigator must contact the Sponsor prior to destroying any records associated with the study. If the Investigator withdraws from the study (due to relocation, retirement, etc.), the records shall be transferred to a mutually agreed upon designee, such as another Investigator or IRB/IEC. Notice of such transfer will be provided in writing to the Sponsor.

9 DATA ANALYSIS METHODS

The statistical and analytical plans presented below summarize the more complete plans to be detailed in the statistical analysis plan (SAP). A change to the data analysis methods described in the protocol will require a protocol amendment only if it alters site conduct (e.g., adding baseline assessments to define a subgroup). The SAP will be finalized prior to DRC review of Cohort 1 data. Any changes to the methods described in the final SAP will be described and justified in the clinical study report.

9.1 Determination of Sample Size

A sample size of 10 subjects at each dose level (4:1 ratio: 8 subjects treated with PT101 and 2 administered placebo) was chosen so that there is a ^{CCI} [REDACTED] to detect a ratio of 2 in the primary PD assessment of the mean change from baseline in the absolute number of peripheral Tregs as measured in whole blood ^{CCI} [REDACTED]

This assumes a one-sided alpha level of 0.1 ^{CCI} [REDACTED]

^{CCI} [REDACTED] At least 30 subjects are expected to be evaluated at Week 12 (planned cohorts 1-3) and a total of approximately 60 subjects will be enrolled in the study.

9.2 Study Endpoint Definitions

See [Section 7.2](#) for definitions of the efficacy/response endpoints.

9.3 Statistical and Analytical Plans

9.3.1 General Considerations

Tabulations will be produced for appropriate demographic, baseline, efficacy, and safety parameters. Continuous variables will be summarized by number of subjects and mean, standard deviation/standard error, median, minimum, and maximum values. Categorical variables will be summarized by number and percentage of subjects. Tests of statistical significance will be described in the SAP.

9.3.1.1 Subject Disposition

The number and percentage of subjects in study populations will be summarized by treatment group, separately for each stage. The subject disposition table will also include the number of subjects screened, randomized, and treated. No formal statistical comparisons will be performed.

Subjects who are screened but not randomized (screen failures) and the associated reasons for failure to randomize will be tabulated for all screened subjects. The number and percentage of subjects who complete the 12-week treatment period and of subjects who prematurely discontinue will be presented for each treatment group and pooled across treatment groups for the Safety Population. The reasons for premature discontinuation from treatment period as recorded in the eCRFs will be summarized.

9.3.1.2 Subject Characteristics

Demographic parameters (age, age group, sex, race, ethnicity, height, weight, body mass index) and other baseline characteristics will be summarized descriptively by treatment group for the intent-to-treat (ITT), full analysis set (FAS), per protocol (PP) analysis set, and safety analysis sets (SAF).

9.3.1.3 Protocol Deviations

Protocol deviations will be summarized by type in each treatment group. Both major and minor protocol deviations will be listed.

9.3.1.4 Prior and Concomitant Therapy

Prior medication is defined as any medication started before the date of study drug administration. A concomitant medication is defined as any medication taken on or after the date of study drug administration.

Prior and concomitant medications will be coded by drug name and therapeutic class using the World Health Organization (WHO) Drug Dictionary. Results will be tabulated by Anatomic

Therapeutic Class and preferred term. If a subject took a specific medication multiple times or took multiple medications within a specific therapeutic class, that subject will be counted only once for the coded drug name or therapeutic class.

9.3.1.5 Randomization and Blinding

Subjects will be randomized in a 4:1 ratio to a PT101 dose level/dosing regimen and placebo. The study will be conducted in a double-blind fashion, which will be described in the Clinical Trial Integrity Plan.

9.3.1.6 Adjustments for Covariates

Detailed methodology will be provided in the SAP.

9.3.1.7 Handling of Dropouts and Missing Data

Detailed methodology will be provided in the SAP.

9.3.1.8 Multiple Comparisons and Multiplicity

No multiplicity adjustments will be applied.

9.3.1.9 Data Transformations and Derivations

Time variables based on 2 dates (e.g., start date and end date) will be calculated as (end date – start date + 1 [in days]) unless otherwise specified in the SAP.

Baseline values used in all statistical analyses will be the most recent non-missing measurement prior to the first dose of study drug unless otherwise specified in the SAP.

More detailed methodology will be provided in the SAP.

9.3.2 Analysis Sets

9.3.2.1 Intent-to-Treat Analysis Set

The ITT analysis set consists of all randomized subjects. Subjects will be included in the treatment group assigned at randomization regardless of the actual treatment received.

9.3.2.2 Full Analysis Set

The FAS consists of all randomized subjects who received any study drug (PT101 or placebo). Treatment groups will be determined using the actual treatment received, regardless of the randomization treatment assignment.

9.3.2.3 Per Protocol Analysis Set

The PP analysis set will consist of all subjects in the FAS who did not have any major protocol violations that might impact the efficacy analyses.

Exclusion of subjects from the PP analysis set will be determined in a final blinded data review meeting that will be held prior to unblinding the randomization list. Reasons for exclusion will be documented for each subject.

9.3.2.4 Safety Analysis Set

The SAF consists of all subjects who receive at least one dose of study drug. Treatment groups will be determined using the actual treatment received, regardless of the randomization treatment assignment. Safety analyses will be performed using the SAF.

Additional analysis sets of subjects may be defined in the SAP.

9.3.3 Examination of Subgroups

As exploratory analyses, subgroup analyses may be conducted for selected endpoints. Detailed methodology will be provided in the SAP.

9.3.4 Safety and Efficacy Analyses

Progression from Cohort 1 to Cohort 2 per protocol will be based on DRC recommendations from all available unblinded safety and PK/PD data reviewed from Cohort 1 along with all unblinded safety data (all 8 subjects [PT101:PBO; 6:2] up to one week after ^{CCI}

^{CCI}
^{CCI}

Recommendations from the DRC may also include modification to the study design, including but not limited to assessment of a lower dose or repeating a dose/dosing regimen, changes to subject safety monitoring assessments or addition of sampling timepoints. ^{CCI}

^{CCI}
^{CCI}

DRC will review all safety and available PK/PD ^{CCI} ons for the next cohort (Cohort 3) regarding study continuation, dose escalation per protocol or any modification to the study design. Moving sequentially from Cohort 1 through 3 will require demonstration of adequate safety, guided by the in-cohort stopping rules and the cohort progression criteria (see [Section 3.1.1.4](#)).

The safety of each dose level will be evaluated by examining the probability of experiencing a DLT (as defined in [Section 3.1.1.3](#)) based on a Bayesian Logistic Regression Model (BLRM) ([Neuenschwander, 2008](#)) and the incidence of TEAEs, TESAEs, treatment-related TEAEs, and treatment-related TESAEs.

A dose will be considered safe if the estimated probability (posterior median) of experiencing a DLT is ≤ 0.25 . The MTD will be determined according to the following rules:

CCI

CCI

The selected dose may not exceed the Escalation With Overdose Control (EWOC) threshold: the posterior probability of overdosing, either excessive or unacceptable toxicity ≤ 0.25 .

The dose level(s) and dosing regimen with the best benefit/risk profile based on the totality of safety and efficacy data at Week 12 will inform selection for future clinical development.

For efficacy endpoints, to compare the proportion of subjects at a timepoint (i.e., Week 12), the Cochran-Mantel-Haenszel (CMH) method will be used and an exact 95% confidence interval will be estimated. CCI

CCI

For continuous data in terms of change from baseline to Week 12, analysis-of-covariance (ANCOVA) on last-observation-carried-forward (LOCF) will be used for analysis. For continuous data with repeated measures postrandomization, mixed-model-repeated measure (MMRM) will be used for analysis. Details on covariates will be specified in the SAP.

All analyses will be descriptive in nature, with point and 95% interval estimates, if necessary, provided for the following parameters of interest, separately for each available PT101 dose level/dosing regimen and placebo unless otherwise specified in the SAP:

- Mean change in total Mayo Scores, modified Mayo Score, RHI score, UC-100 score, and PROs (IBDQ, SF-36) at Week 12
- Mean change from baseline in partial Mayo Score, FC, and hs-CRP levels at assessed timepoints through Week 12
- Mean change from baseline in partial Mayo Score beyond Week 12

- Proportion of subjects achieving clinical remission, endoscopic improvement, clinical response, endoscopic remission, histologic remission, histologic response, mucosal healing at Week 12
- Proportion of subjects achieving symptomatic remission and symptomatic response at assessed timepoints through Week 12

9.3.5 Exploratory Efficacy Analyses

MMRM may be used to compare change from baseline in partial Mayo Score beyond Week 12 as well as change in PT101- and UC-associated biomarkers.

9.3.6 Pharmacokinetic and Immunogenicity Analyses

9.3.6.1 Pharmacokinetic Analyses

Serum concentrations of PT101 will be listed and summarized by treatment group using descriptive statistics (sample size, arithmetic mean, geometric mean, % coefficient of variation, standard deviation, median, minimum, and maximum). Concentration over time may also be plotted in semilogarithmic and linear formats.

ADA to PT101 will be assessed using a standard 3-tier approach to measure binding antibody with a screening assay, ADA titer using a confirmatory assay, and neutralizing antibody to PT101 in subjects with confirmed positive titers. Data will be listed and summarized by treatment group as detailed in the SAP.

9.3.6.2 Biomarker Analyses

Relationships of biomarker parameters (e.g., baseline values, absolute and relative changes from baseline) to efficacy, safety, and PK parameters will be explored. Relationships and associated data that are determined to be of interest will be summarized. Details will be described separately in the SAP.

9.3.7 Safety Analyses

The safety analyses will be performed using the SAF. The safety parameters will include AEs and SAEs, vital sign measurements, ECG findings and clinical laboratory values. The primary safety analysis will include all data available for all subjects through Week 12.

9.3.7.1 Extent of Exposure

Duration of treatment will be summarized and listed. Duration of treatment, number of doses, and total dose will be summarized. Dose modifications will also be summarized.

9.3.7.2 Adverse Events

An overview of AEs will provide a tabulation of the incidence of all AEs, treatment-emergent AEs, treatment-related AEs, Grade 3 and higher AEs, SAEs, treatment-related SAEs, deaths,

and AEs leading to study treatment discontinuation. Adverse events will be defined as treatment emergent if they are newly occurring or worsen following study treatment.

AEs will be listed and summarized by Medical Dictionary for Regulatory Activities (MedDRA), preferred term, severity, and relationship to study drug. In the event of multiple occurrences of the same AE with the same preferred term in 1 subject, the AE will be counted once as the occurrence. The incidence of AEs will be tabulated by preferred term and treatment group. AEs leading to premature discontinuation of study drug will be summarized and listed in the same manner.

9.3.7.3 Deaths and Serious Adverse Events

SAEs will be listed and summarized in the same manner as all AEs. Events with a fatal outcome will be listed.

9.3.7.4 Clinical Laboratory Results

Laboratory values (e.g., chemistry, hematology, and urinalysis) may be presented graphically by visit. Summary statistics may be tabulated as appropriate by scheduled visit. Laboratory values will be listed with grade per NCI CTCAE and flagged when values are outside the normal reference range.

9.3.7.5 Other Safety Analyses

Vital Signs

Vital signs will be presented graphically for each vital sign by scheduled visit. Summary statistics and change from baseline and/or predose to postdose may be tabulated where appropriate.

ECG

ECG status (normal, abnormal clinically significant, or abnormal not clinically significant) may be summarized for each scheduled ECG, and shifts from baseline may be tabulated.

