 - New onset of clinically significant cardiovascular disease such as myocardial infarction, unstable ischemic heart disease, stroke, heart failure, or clinically significant changes in ECG
 - Subjects with a marked prolongation of the QTc interval identified on ECG during the study (e.g., increase in QTc to > 500 ms, or > 60 ms over baseline, [Appendix 8](#))
 - New onset of pulmonary edema, interstitial lung disease, or clinically significant dyspnea
 - New onset of clinically significant peripheral edema or reduced blood pressure (semi recumbent [supine or seated also acceptable, per site standard procedures]) SBP < 90 mmHg associated with symptoms such as lightheadedness, sustained over at least the next 90 minutes):

- SBP (supine or seated also acceptable) will be obtained as triplicate measurements every 30 minutes over the following 90 minutes (i.e. at 30, 60- and 90 minutes). If a subject's SBP remains < 90 mmHg for the median of all 3 measurements over the 90 minute period, this is defined as a sustained finding, and dosing will end for that particular subject.
- Reduction of estimated glomerular filtration rate (eGFR) < 60 mL/min confirmed on repeat measurement after at least 24 hours
- Serious infection requiring hospitalization or intravenous antibiotics
- Investigator or Sponsor determines that the subject will not benefit from further study drug
- Adverse event or laboratory or physical examination finding that in the opinion of the Investigator or Sponsor presents excessive risk to the subject
- Adverse event of Grade 3 or higher in severity that is attributable to study drug, or any unexplained \geq Grade 3 AE that is not reasonably related to the underlying disease process
- Subject becomes pregnant or plans a pregnancy within the study conduct
- Subject is unable to comply with the protocol requirements
- Sponsor or Regulatory Agency terminates the study

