#### 4.3 HANDLING OF DATA

In general, missing data will not be imputed unless methods for handling missing data are specified. For purposes of the DRC safety assessment, all results will be presented ‘as observed’ with missing values not imputed. The handling of missing data in analyses of the efficacy endpoints is discussed in Section 6.2.4.

If multiple valid, non-missing, continuous measurements or visits (regardless if it’s scheduled or unscheduled) occurring within a single visit, records will be chosen based on the following rules if a single value is needed:

- For baseline, the baseline value will be the last non-missing value prior to the first dosing of study drug; if multiple measurements occur on the same day, the last non-missing value prior to the time of first dosing of study drug will be considered as the baseline value. If these multiple measurements occur at the same time or the time is not available, the average of these measurements will be considered the baseline value.
- For post-baseline values:
  - a. The record closest to the nominal day for that visit will be selected.
  - b. If there are 2 records that are equidistant from the nominal day, the later record will be selected.
  - c. If there is more than 1 record on the selected day, the average will be taken.

If multiple valid, non-missing, categorical observations exist for one visit, records will be selected as follow:

- For baseline, the last available record prior to the first dose of study drug will be selected. If there are multiple records at the same time or no time recorded on the same day, the worst value will be selected unless otherwise specified.
- For post-baseline values:
  - a. The record closest to the nominal day for that visit will be selected.
  - b. If there are 2 records that are equidistant from the nominal day, the later record will be selected.
  - c. If there is more than 1 record on the selected day, the value with the worst severity will be used.

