### 9.3 VITAL SIGNS

Descriptive statistics will be provided by treatment group for vital signs (blood pressure (mm Hg), heart rate (bpm), respiratory rate, temperature, and weight (kg), as follows:

- Baseline values
- Values at each post-baseline visit
- Change from baseline at each post-baseline visit

A by-subject listing of vital signs will be provided by treatment group, subject ID number, and visit in chronological order.

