- Section 9: Safety Analyses: Overall summary of TEAEs, TEAEs by SOC and PT, TEAEs by SOC, PT and maximum severity, severe (CTCAE Grade  $\geq 3$ ) TEAEs by SOC and PT, Related TEAEs by SOC and PT, TESAEs by SOC and PT, descriptive statistics for ECGs, vital signs, clinical laboratory parameters.
- Section 13.1: Assessment of Dose-Limiting Toxicity: Overall listing of dose-limiting toxicity (DLT) AE's.

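### SAP 4.3 averages all same-day vital-sign readings into one visit value, so the planned tables understate an acute, mainly transient, fall in blood pressure

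*Protocol*

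**What the plan says.** Change in vital signs is part of the primary endpoint (protocol 2.2.1). On its analysis, protocol 9.3.7.5 says: "Summary statistics and change from baseline and/or predose to postdose may be tabulated where appropriate".

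Protocol 7.6.6 takes heart rate and blood pressure as single measurements at the times in the schedule of events, which is redacted. Protocol 6.3.1 puts safety procedures before dosing unless otherwise specified. The readable source of repeated same-day readings is protocol 3.1.7. When new-onset SBP below 90 mmHg comes with symptoms, pressure "will be obtained as triplicate measurements every 30 minutes over the following 90 minutes", that is, at 30, 60 and 90 minutes.

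SAP 9.3 plans baseline values, values at each post-baseline visit, and "Change from baseline at each post-baseline visit". It also keeps a listing: "A by-subject listing of vital signs will be provided by treatment group, subject ID number, and visit in chronological order".

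SAP 4.3 covers several continuous records within one visit, "regardless if it’s scheduled or unscheduled". It says that "records will be chosen based on the following rules if a single value is needed". For post-baseline values the record nearest the nominal day is taken, and then: "If there is more than 1 record on the selected day, the average will be taken".

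SAP 13 names, among the analyses that may go to the DRC, "descriptive statistics for ECGs, vital signs, clinical laboratory parameters".

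**The concern.** A table of values and changes by visit needs one number per subject per visit, so the condition in SAP 4.3 is met unless the SAP defines separate timepoints within the visit. It does not. A low reading is then averaged with whatever else was recorded that day: a predose reading on a later dosing day, any post-dose readings, and the unscheduled rechecks.

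For most vital-sign data this is harmless, because there is one record. It matters for an acute fall in blood pressure, which is what repeated readings are taken to document. Symptomatic low SBP is one of the protocol's individual stopping criteria. Laboratory tests and ECGs have shift tables in the SAP; vital signs have no shift, threshold or worst-value summary to offset the averaging. The summary tables for part of the primary endpoint, and the descriptive statistics that may go to the DRC, could therefore show a smaller effect than was measured.

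**Working it through.** The plan gives no figure to reproduce, so the check is of what the averaging rule does.

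**Inputs from the documents.** The same-day mean, scheduled and unscheduled records together (SAP 4.3). Baseline is the last value before first dose (SAP 4.1, 4.3). Rechecks: 3 readings × 3 times = 9, plus the reading that triggered them (protocol 3.1.7). Eight PT101 subjects per cohort (protocol 9.1).

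**Assumed values** (the documents hold no blood pressure data): baseline and predose SBP 120 mmHg, low SBP 85 mmHg, recovered SBP 120 mmHg. The measured fall is 85 − 120 = −35 mmHg. Rechecks are assumed to be entered as vital-sign records.

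**Formula.** With N records on the day, L of them low and the rest at baseline, tabulated change = fall × L/N. The fraction kept depends only on the counts.

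| Same-day records | L/N | Visit value (mmHg) | Tabulated change (mmHg) | Kept |
|---|---|---|---|---|
| 1 predose, 1 low | 1/2 | 102.5 | −17.5 | 50% |
| 1 predose, 2 low | 2/3 | 96.7 | −23.3 | 67% |
| 1 predose, trigger and 9 rechecks all low | 10/11 | 88.2 | −31.8 | 91% |
| 1 predose, 1 low, 1 recovered | 1/3 | 108.3 | −11.7 | 33% |
| 1 predose, 1 low, 3 recovered | 1/5 | 113.0 | −7.0 | 20% |
| 1 predose, 1 low, 9 recovered | 1/11 | 116.8 | −3.2 | 9% |

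**Day 1 differs.** The last predose reading is the baseline, and the rule covers post-baseline values only, so it is not averaged in. A sustained fall is then kept in full (10/10), but a single low reading with nine recovered rechecks keeps 1/10: (85 + 9 × 120)/10 = 116.5, a change of −3.5 mmHg.

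**Effect on a group mean.** If one of eight subjects falls by 35 mmHg and the others do not change, the mean moves by 35/8 = 4.4 mmHg without averaging, 17.5/8 = 2.2 at 50% kept, and 3.2/8 = 0.4 at 9% kept. A single event is hard to see in a mean even without averaging, so separating the readings needs to be paired with a per-subject lowest value and a count.

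**The case against.** Several stronger readings are tempting, and the documents do not support them.

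- **That the SAP breaks a protocol commitment.** The protocol offers predose-to-postdose change as an alternative that may be used where appropriate, and the SAP tabulates change from baseline. This is a declined option, so the silence of SAP 14 is not a fault.
- **That any SBP below 90 mmHg brings nine more readings.** The rule in protocol 3.1.7 also requires symptoms. The repeated readings that can be seen in the text are therefore confined to a few subjects.
- **That predose and post-dose readings are routinely averaged.** The schedule is redacted and the readable default is predose. If only a predose reading exists, there is nothing to average. The one-predose, one-post-dose row applies only if the schedule includes post-dose readings.
- **That an acute fall disappears, or that dose decisions rest on the averaged tables.** The listing is kept. Sustained symptomatic hypotension ends dosing, so it would be expected among discontinuations and adverse events. The DRC may also receive adverse event summaries and a listing of DLTs; the readable escalation criteria use DLTs and the stopping rules, not mean vital signs. The full DRC package is set in a charter that is not available.

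All of this stands, and it limits the point. It does not remove it: the averaging rule is stated, nothing in SAP 9.3 exempts vital signs, and the loss is largest for transient falls. A transient symptomatic fall may be reported as an adverse event but, not being sustained, would not meet the hypotension criterion for discontinuation. Its size would be readable only in the listing.

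**Conclusion.** The point holds as a modest, cheap improvement to the SAP. Under the stated rule, summary tables understate an acute same-day fall in blood pressure wherever several readings exist that day. Transient falls are affected most (about 9% to 33% kept with one predose and one to nine recovered readings). A single predose and post-dose pair keeps 50%, and a sustained fall with all rechecks low loses little (about 91% kept).

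These fractions follow from the counts of readings if the other readings sit at baseline; the mmHg values are illustrative. How often the situation arises cannot be determined: it depends on how many subjects meet the symptomatic trigger and on post-dose times that are redacted. The conclusion is about the summary tables only, not about whether events are captured in the trial.

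**What to change.** In SAP 4.3 and 9.3, exempt vital signs from same-day averaging across predose, post-dose and unscheduled recheck readings. Where both predose and post-dose readings are collected, summarise them as separate timepoints and tabulate the within-day change.

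Add one descriptive table per treatment group, also supplied to the DRC: the lowest post-baseline SBP per subject, and the number of subjects with any post-baseline SBP below 90 mmHg, both including unscheduled readings. The 90 mmHg cut is the protocol's own and is used here only for counting; no clinical rule changes.

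The cost is a few sentences of SAP text and one extra table. No new measurements are needed, provided the rechecks are entered in the database.
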